11.2. Follow-Up after Early Study Drug Discontinuation/Lost to Follow-Up

- Patients who prematurely discontinue study drug are not to be replaced.
- All randomized patients must be followed up according to the study flowchart until the study end date or death, regardless of whether they discontinue study drug prematurely or not. Any event occurring after early study drug discontinuation will be recorded up through the study end date.
- In order to follow the medical status of the patients, especially when they withdraw after having experienced an adverse event, investigators are encouraged to obtain information from the patient's primary care practitioner (physician or any other medical care provider). Investigators are also requested to try as much as possible to re-contact those patients at the end of the trial to obtain at least their vital status as well as their status with respect to the primary endpoint, and thus avoid lost to follow-up for the efficacy assessment.
- If patients are lost to follow-up, the CRF must be completed up to the last visit or contact. Patients who didn't have a study visit for 1 year or longer are considered lost to follow-up.

12. STATISTICS

12.1. Analysis Populations

12.1.1. Randomized Population

The randomized population will include all patients who sign the informed consent form and are assigned a randomization number at Visit 2 (Day 0).

12.1.2. Intent-to-Treat Population

The Intent-to-Treat (ITT) population will consist of all randomized patients who take at least one dose of study drug. The ITT population is the primary analysis population. All efficacy analyses will be performed on the ITT population.

12.1.3. Per-Protocol Population

The per-protocol (PP) population will include all ITT patients without any major protocol deviations, and who had $\geq 80\%$ compliance with study drug while on treatment (up to discontinuation for patients whose treatment is terminated early). The per-protocol efficacy analysis for CV events will be restricted to each patient's time on study drug plus 30 days thereafter.

12.1.4. Safety Population

All safety analyses will be conducted based on the safety population, which is defined as all randomized patients who receive at least one dose of study drug. This is the same as the ITT population.

12.2. Statistical Methods

Safety and efficacy variables will be analyzed using appropriate statistical methods to be described in detail in a separate Statistical Analysis Plan (SAP). The SAP will be finalized before study unblinding.

12.2.1. Patient Disposition and Demographic/Baseline Characteristics

The numbers of patients screened, the number of patients randomized per treatment group (randomized population), and the number of patients in the ITT and PP populations by treatment group will be listed.

For randomized patients who discontinued treatment with study drug, the primary reason for discontinuation will be listed and summarized by treatment group.

Summary statistics (mean, standard deviation, median, minimum and maximum) will be provided by treatment group for demographic characteristics (e.g., age, sex, race, and ethnicity) and baseline characteristics (e.g., body weight, height, and body mass index) in the ITT and PP populations.

Demographic data and baseline characteristics will be compared among treatment groups for the ITT and PP population. Differences in demographic and baseline characteristics will be tested using a chi-square test (for categorical variables) or a 1-way analysis of variance model with treatment as a factor (for continuous variables). The p-values will be used as descriptive statistics, primarily as an assessment of the adequacy of randomization.

12.2.2. Study Medication Exposure and Compliance

The final compliance to study drug will be calculated as the percent of doses taken relative to doses scheduled to be taken. Overall percent compliance will be calculated per patient in the ITT and PP populations and summarized by treatment group using summary statistics (n, mean, standard deviation, median, minimum, and maximum).

12.2.3. Concomitant Therapies

Concomitant medication/therapy verbatim terms will be coded using the latest version of the World Health Organization Drug Dictionary. The numbers and percentages of patients in each treatment group taking concomitant medications will be summarized by anatomic and therapeutic chemical classification and preferred term.

12.2.4. Analysis of Efficacy

For efficacy endpoints including CV events, only adjudicated events will be included in the final statistical analyses.

12.2.4.1. Summary Statistics

Summary statistics (n, mean, standard deviation, median, minimum, and maximum) for the baseline and post-baseline measurements, the percent changes, or changes from baseline will be presented by treatment group and by visit for all efficacy variables to be analyzed. The summary statistics will include changes in body weight and body mass index from baseline by treatment group and by visit.

12.2.4.2. Primary Endpoint

The primary efficacy endpoint is the time from randomization to the first occurrence of any component of the composite of the following clinical events:

- CV death,
- Nonfatal MI (including silent MI),
- Nonfatal stroke,
- Coronary revascularization,
- Hospitalization for unstable angina determined to be caused by myocardial ischemia by invasive/non-invasive testing.

The analysis of the primary efficacy endpoint will be performed using the log-rank test comparing the 2 treatment groups (AMR101 and placebo) and including the stratification factor “CV risk category”, use of ezetimibe and by geographical region (Westernized, Eastern European, and Asia Pacific countries) as recorded in the IVRS at the time of enrollment. Treatment difference will be tested at alpha level of 0.0476 accounting for one interim efficacy analysis. The hazard ratio for treatment group (AMR101 vs. placebo) from a Cox proportional hazard model that includes the stratification factor will also be reported, along with the associated 95% confidence interval. Kaplan-Meier estimates from the time to the primary efficacy endpoint will be plotted.

12.2.4.3. Secondary Endpoints

The statistical analyses of the secondary endpoints will be analyzed by the same log-rank test specified above for the primary efficacy endpoint. Treatment differences will be tested at alpha level of 0.05 using a sequential procedure for controlling type 1 error starting with the key secondary variable. The remaining secondary variables will be tested in the order specified in [Section 9.2.2](#). Estimates of the hazard ratios from the Cox proportional hazard and the associated 95% confidence intervals will also be provided. Kaplan-Meier estimates from the time to the secondary efficacy endpoints will be plotted.

12.2.4.4. Tertiary Endpoints

For event rates, the statistical analyses of the tertiary endpoints will be similar to the analysis of the secondary efficacy endpoints.

For measurements of lipids, lipoproteins and inflammatory markers the change from baseline will be analyzed in the units of each marker, and the percent change from baseline.

New onset diabetes is defined as Type 2 diabetes newly diagnosed during the treatment/follow-up period (i.e. patients with no history of diabetes at randomization, with the test as listed in [Appendix C](#)).

12.2.4.5. Subgroup Analyses

The following subgroups will be explored. Log-rank tests, treatment effects and the associated 95% confidence intervals for the primary and secondary efficacy endpoints within each subgroup will be provided using the Cox proportional hazard model with treatment (AMR101 or placebo), and stratification as a factor (with the exception of the subgroup analyses of those subgroup variables related to the stratification factors, i.e., CV risk category that will not have stratification as a factor):

- Gender,
- age (<65 yr and ≥ 65 yr),
- race (white and nonwhite, or any other subset with at least 10% of the total number of patients),
- CV risk category (previous CV disease or not),
- the presence/absence of diabetes at baseline,
- baseline LDL-C (by tertile),
- baseline HDL-C (by tertile),
- baseline TG (by tertile),
- hs-CRP (≤ 3 mg/L and >3 mg/L),
- Apo B (by tertile)

The consistency of the treatment effects in subgroups will be assessed for the primary and secondary efficacy endpoints. For each subgroup variable, a Cox proportional hazard model with terms for treatment, stratification factors (with the exception of those subgroup variables related to the stratification factors, i.e., CV risk category), subgroup, and treatment-by-subgroup interaction will be performed. The main treatment effect will not be tested with this model. P-values for testing the interaction terms will be provided.

12.2.4.6. Interim Efficacy Analysis

One interim analysis will be performed for the primary efficacy endpoint using best available data (adjudicated events and site reported endpoints) based on data when approximately 60% of the total number of primary endpoint events is reached. The interim analysis will be based on a group sequential design that includes early stopping rules for benefit while preserving the overall Type I error rate (O'Brien-Fleming). This allows for interim analysis and preserves the overall Type I error probability of $\alpha=0.05$ for the primary endpoint.

Approximately 1612 events are planned to be observed during the trial, based on sample size calculation assumptions. Therefore, the interim analysis will occur after at least 967 events have been observed. According to this boundary, the critical p-value at the interim analysis has to be $p \leq 0.0076$, resulting in the final evaluation p-value of 0.0476.

The interim results of the study will be monitored by an independent DSMB. The analyses will be performed by the independent statistical group unblinded to the treatment assignment. The results will be reported only to the DSMB. The unblinded information will not be released to sponsor under any circumstance before the completion of the study. Specific statistical guidelines for data monitoring will be discussed and formalized in a separate Interim Statistical Analysis Plan and DSMB Charter.

12.2.5. Analysis of Safety

All analyses of safety will be conducted on the safety population, which is defined as all randomized patients who receive at least one dose of study drug. The safety assessment will be based on the frequency of adverse events, physical exams, vital signs and safety laboratory tests.

Adverse events with new onset during the study between the initiation of study drug and 30 days after the last dose of study drug for each patient will be considered treatment-emergent (TEAEs). This will include any AE with onset prior to initiation of study drug and increased severity after the treatment initiation.

Treatment-emergent adverse events will be summarized by system organ class and preferred term, and by treatment. This will include overall incidence rates (regardless of severity and relationship to study drug), and incidence rates for moderate or severe adverse events. A summary of SAEs, and adverse events leading to early discontinuation from the study will be presented through data listings.

Safety laboratory tests and vital signs will be summarized by post-treatment change from baseline for each of the parameters using descriptive statistics by treatment group. Those patients with significant laboratory abnormalities will be identified in data listings. Additional safety parameters will be summarized in data listings.

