ligation (McLennan 1992; Leaf 1996). In isolated cells, the story is similar (Li 1997, Engler 2000; Omura 2001). In neonatal rat cardiac myocytes, EPA prevents the arrhythmogenic action of many interventions, including high external Ca^{2+} and ouabain (Kang 1994). The antiarrhythmic effect is caused by a reduction in electrical excitability caused by partitioning O3FAs into the phospholipid cell membranes of the cardiac myocytes, which modulates membrane ion channels. This is the postulated direct mechanism that refers to the antiarrhythmic effect of O3FAs which inhibits the fast, voltage-dependent sodium current along with the L-type calcium currents. This reduces the action potential of cardiac myocytes, reducing the susceptibility to arrhythmia. These cellular alterations are likely to reduce the severity of ventricular arrhythmias by inhibiting the rapid accumulation of intracellular Ca^{2+} following ischemia. It was also shown in patients with coronary artery disease that long-term treatment with EPA augments both NO-mediated and non-NO-mediated endothelium-dependent forearm vasodilatation (Tagawa 1999).

Another, indirect mechanism refers to the effect of O3FAs on cardiac arrhythmias by modifying the balance of different eicosanoids which are produced as end-products from chain elongation of their parent polyunsaturated fatty acids (Nair 1997). Most investigations of the link between O3FAs and heart disease have demonstrated the competition between AA and O3FAs to become substrates in the production of eicosanoids. O3FAs compete with AA in several ways, but EPA in particular competes with AA as the substrate for the cyclooxygenase enzyme inhibiting the production of thromboxane A_2 (TXA_2) and in endothelial cells, prostaglandin I_3 (PGI_3) is synthesized from EPA (Nair 1997). The net result of these actions is vasodilatation. A reduced ratio of AA/EPA shifts the spectrum of eicosanoid production toward an increase in thromboxane A_3 (TXA_3) and PGI_3 at the expense of TXA_2 and PGI_2 , respectively. This shift was found to reduce the risk of ventricular fibrillation (VF) and sudden cardiac death (SCD) (Coker 1982). Excessive production of eicosanoids derived from omega-6 fatty acids have been associated with heart attacks, thrombotic stroke, and arrhythmia, while those from O3FAs are antiarrhythmic.

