6.3.2.7. Electrocardiogram (ECG)

ECGs (standard 12-lead) will be obtained annually. Site personnel should make every attempt to perform a patient's ECG using the same equipment at each visit. ECGs will be reviewed by the site for the detection of silent MI. Silent MIs will be sent for event adjudication.

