10. SAFETY ASSESSMENTS

10.1. Specification of Variables and Procedures

Safety assessments will include adverse events, clinical laboratory measurements (chemistry, hematology), 12-lead ECGs, vital signs (systolic and diastolic blood pressure, heart rate, respiratory rate, and oral body temperature), and physical examinations as per Study Procedures/[Appendix A](#).

A complete medical, surgical and family history will be completed at Visit 1.

A list of the analytes to be measured for the safety evaluation is found in [Section 6.3.1.1](#). All laboratory test results must be evaluated by the investigator as to their clinical significance. Any observations at physical examinations or laboratory values considered by the investigator to be clinically significant should be considered an adverse event.

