Beneficial effects in clinical trials have been attributed in part to reducing arrhythmias (Lee 2003; Goel 2002; Calo 2005). The case for an antiarrhythmic effect of O3FAs comes from clinical trials and from animal studies. Clinical trials have shown that the risk of sudden death in patients who have survived myocardial infarction is greatly reduced by inclusion of O3FAs in the diet (Siscovick 2000). Thus it seems that fatal ventricular fibrillation is less likely to occur during sufficient intake of O3FAs. Animal studies support this. Coronary ligation studies in a variety of species (rats, dogs and marmosets) have shown that the incidence of ventricular fibrillation is lower in animals fed a diet rich in O3FAs before ligation (McLennan 1992; Leaf 1996). In isolated cells, the story is similar (Li 1997, Engler 2000; Omura 2001). In neonatal rat cardiac myocytes, EPA prevents the arrhythmogenic action of many interventions, including high external Ca^{2+} and ouabain (Kang 1994). The antiarrhythmic effect is caused by a reduction in electrical excitability caused by partitioning O3FAs into the phospholipid cell membranes of the cardiac myocytes, which modulates membrane ion channels. This is the postulated direct mechanism that refers to the antiarrhythmic effect of O3FAs which inhibits the fast, voltage-dependent sodium current along with the L-type calcium currents. This reduces the action potential of cardiac myocytes, reducing the susceptibility to arrhythmia. These cellular alterations are likely to reduce the severity of ventricular arrhythmias by inhibiting the rapid accumulation of intracellular Ca^{2+} following ischemia. It was also shown in patients with coronary artery disease that long-term treatment with EPA augments both NO-mediated and non-NO-mediated endothelium-dependent forearm vasodilatation (Tagawa 1999).

Another, indirect mechanism refers to the effect of O3FAs on cardiac arrhythmias by modifying the balance of different eicosanoids which are produced as end-products from chain elongation of their parent polyunsaturated fatty acids (Nair 1997). Most investigations of the link between O3FAs and heart disease have demonstrated the competition between AA

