6.3.2.7. Electrocardiogram (ECG)

ECGs (standard 12-lead) will be obtained annually. Site personnel should make every attempt to perform a patient's ECG using the same equipment at each visit. ECGs will be reviewed by the site for the detection of silent MI. Silent MIs will be sent for event adjudication.

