12.2.5. Analysis of Safety

All analyses of safety will be conducted on the safety population, which is defined as all randomized patients who receive at least one dose of study drug. The safety assessment will be based on the frequency of adverse events, physical exams, vital signs and safety laboratory tests.

Adverse events with new onset during the study between the initiation of study drug and 30 days after the last dose of study drug for each patient will be considered treatment-emergent (TEAEs). This will include any AE with onset prior to initiation of study drug and increased severity after the treatment initiation.

Treatment-emergent adverse events will be summarized by system organ class and preferred term, and by treatment. This will include overall incidence rates (regardless of severity and relationship to study drug), and incidence rates for moderate or severe adverse events. A summary of SAEs and adverse events leading to early discontinuation from the study will be presented through data listings.

Safety laboratory tests and vital signs will be summarized by post-treatment change from baseline for each of the parameters using descriptive statistics by treatment group. Those patients with significant laboratory abnormalities will be identified in data listings. Additional safety parameters will be summarized in data listings.

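### 12-lead ECGs are declared a safety assessment, but the safety analysis plans no between-arm summary of them, so ECG changes short of hospitalization or clinical significance go uncompared

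*Combined protocol and SAP*

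**What the plan says.** Section 10.1 is the same on this point in the 2011 protocol and in Amendment 1: "Safety assessments will include adverse events, clinical laboratory measurements (chemistry, hematology), 12-lead ECGs, vital signs" and physical examinations. Section 6.3.2.7 sets the frequency, "ECGs (standard 12-lead) will be obtained annually", and gives one purpose for the site reading: "ECGs will be reviewed by the site for the detection of silent MI". Appendix A places ECGs at Visit 1, at Visit 2 (Day 0), at Visits 4 to 7 (Days 360, 720, 1080 and 1440) and at the last visit.

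Section 12.2.5, also the same in both versions, sets the basis of the safety analysis: "The safety assessment will be based on the frequency of adverse events, physical exams, vital signs and safety laboratory tests". By-arm change from baseline is promised for two groups of measurements: "Safety laboratory tests and vital signs will be summarized by post-treatment change from baseline for each of the parameters using descriptive statistics by treatment group". Anything else falls under a general clause: "Additional safety parameters will be summarized in data listings".

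The rationale (Section 1.5, Pleiotropic Effects) describes a postulated antiarrhythmic action of omega-3 fatty acids on cardiac cell membranes, "which modulates membrane ion channels", and says that it "inhibits the fast, voltage-dependent sodium current along with the L-type calcium currents".

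**The concern.** A measurement that the protocol itself classes as a safety assessment has no place in the safety analysis. The ECGs are taken on schedule in every patient and read by blinded site staff. That makes them less dependent on who reports a symptom than adverse event data are. A listing prints individual records; it gives no denominators and no comparison between groups.

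The question is a natural one for this product, because the sponsor's own rationale appeals to an effect on cardiac electrical activity. At stake is an ECG-visible shift in rhythm or conduction, in either direction, that is too mild to cause a hospitalization or to be called clinically significant. Followed as written, the plan would collect tracings that could show such a shift and never set the two arms side by side.

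**Working it through.** The plan gives no figure to reproduce. The check is mainly a comparison of text, followed by illustrative arithmetic on what a table could show.

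**1. Declared against analysed (both versions)**

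| Item | Declared in 10.1 | In the basis of 12.2.5 | By-arm summary stated in 12.2.5 |
|---|---|---|---|
| Adverse events | Yes | Yes | Yes, by organ class, preferred term and treatment |
| Safety laboratory tests | Yes | Yes | Yes, change from baseline |
| Vital signs, including heart rate | Yes | Yes | Yes, change from baseline |
| Physical examinations | Yes | Yes | None stated |
| 12-lead ECGs | Yes | No | None; listings at most |

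ECGs are the only declared item left out of the basis altogether.

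**2. Rhythm and conduction outcomes that are compared by arm**

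- Cardiac arrhythmia requiring hospitalization is part of an ordered secondary composite (9.2.2) and is a tertiary endpoint (9.2.3). Cardiac arrest is also tertiary. Sections 12.2.4.3 and 12.2.4.4 apply log-rank tests and Cox hazard ratios.
- Amendment 1, Appendix B, 23.12 defines the arrhythmia endpoint. It covers atrial and ventricular arrhythmia, and bradyarrhythmia (including second- and third-degree AV block) that requires pacing.
- Section 10.2 turns clinically significant abnormal assessments into adverse events, which 12.2.5 tabulates by treatment.
- Heart rate is a vital sign (6.3.2.3) and is summarized by arm.

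**3. What these routes leave out**

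- The endpoint route needs a hospitalization and, for bradyarrhythmia, pacing as well. First-degree AV block and bundle-branch block are outside the definition.
- The adverse event route needs an investigator to judge the finding clinically significant. The sentence in 10.1 that turns findings into adverse events names physical examinations and laboratory values, not ECGs; the broader wording in 10.2 has to cover them.
- The uncovered remainder is a new ECG finding that meets neither condition.

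**4. Volume of data**

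The shortest planned follow-up is 3.25 years, about 3.25 × 365 = 1186 days, so the Day 1080 visit falls within it for every patient. Baseline plus Days 360, 720 and 1080 gives 4 × 7990 = 31,960 tracings before attrition. Screening, Day 1440 and last-visit ECGs come on top.

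**5. What a by-arm table of new findings could show**

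The event rates and the lower values of m are assumptions. The upper m is the planned 3995 per arm (Section 3.6). With two-sided alpha 0.05, unpooled:

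power = Φ( |p1 − p2| / √{[p1(1 − p1) + p2(1 − p2)]/m} − 1.96 )

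- 2% v 3% (variance sum 0.0196 + 0.0291 = 0.0487):
  - m = 3000: 0.01/0.00403 = 2.48, power 0.70
  - m = 3500: 0.01/0.00373 = 2.68, power 0.76
  - m = 3995: 0.01/0.00349 = 2.86, power 0.82
- 3% v 4% (variance sum 0.0291 + 0.0384 = 0.0675):
  - m = 3000: 0.01/0.00474 = 2.11, power 0.56
  - m = 3500: 0.01/0.00439 = 2.28, power 0.62
  - m = 3995: 0.01/0.00411 = 2.43, power 0.68

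**6. If printed intervals were also captured**

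For a change in QTc from baseline to Year 1, the 95% half-width of the arm difference is 1.96 × SD × √(2/m). The SD is assumed:

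- SD 15 ms, m = 3500: 0.70 ms
- SD 20 ms, m = 3000: 1.01 ms
- SD 25 ms, m = 3000: 1.27 ms

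**The case against.** The strongest reply is that the rhythm and conduction events that matter most clinically are already compared. Hospitalized arrhythmia and cardiac arrest are endpoints, a clinically significant new arrhythmia or block on a routine ECG becomes an adverse event tabulated by treatment, and heart rate is summarized as a vital sign. All of that stands. A reader might infer from 12.2.5 that an effect on rhythm or conduction is never compared between arms; the endpoint and adverse event sections contradict that.

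Three further points also stand.

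- A reader might take 6.3.2.7 to mean that sites look for silent MI and nothing else. The text states that purpose and no other, but it does not exclude others, and 10.2 still obliges sites to report significant findings.
- A reader might infer that the protocol itself predicts changes in PR, QRS or QT. It does not mention those intervals. It describes an antiarrhythmic effect of omega-3 fatty acids as a class, calls the direct mechanism postulated, and draws on isolated-cell and animal work. Concern about intervals is an inference from that text.
- Section 12.2 defers detailed safety methods to a separate SAP. Neither that SAP nor the body of Amendment 2 is in the document reviewed, so an ECG analysis may have been specified later.

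The reply does not remove the remainder in step 3. Nor does deferral to a SAP fully answer it: a SAP can tabulate only what the CRF recorded, and no section calls for rhythm or conduction findings to be recorded when the tracing is read.

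**Conclusion.** The point holds in a limited form. In both available versions, 12-lead ECGs are declared a safety assessment and then omitted from the safety analysis. ECG-detected rhythm and conduction changes that are neither hospitalized nor judged clinically significant therefore have no planned between-arm summary. The inconsistency rests on the text alone and needs no assumption.

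The size of the loss does rest on assumptions. About 32,000 planned tracings would yield no comparison of such findings. A table could have moderate to good power, 0.56 to 0.82, for a one-percentage-point difference at the assumed rates. These figures show that the table would be informative; they are not evidence of harm. Nothing here bears on the primary analysis or on type I error. It is a cheap improvement to the safety reporting, subject to what the SAP and Amendment 2 contain.

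**What to change.** - **Section 12.2.5:** add 12-lead ECGs to the basis of the safety assessment. Specify a table by treatment group for each scheduled ECG visit, with the number and percentage of patients who have a finding not present at baseline: new non-sinus rhythm, new AV block, new bundle-branch block. Use as denominator the patients with a readable ECG at baseline and at that visit.
- **Section 6.3.2.7 and the CRF:** have the site record rhythm and conduction findings when it reads the tracing for silent MI.
- **Optional:** where the machine-printed PR, QRS and QT/QTc are captured, add their change from baseline by arm. This is more debatable than the table of findings, because it adds interval fields to every tracing.

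Stating in 10.1 that ECGs serve only silent-MI detection and adverse event reporting would remove the contradiction, but it would leave the gap.

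The cost is a few CRF fields and one set of safety tables. No extra ECG, reader or core laboratory is needed. Site and machine readings are noisier than core-laboratory readings. With both arms blinded the noise should be equal between them, so it would tend to dilute a difference rather than create one.
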